5.1 Schedule

All patients will be registered through CORe.

The Phase Ib dose escalation stage of the study will evaluate the safety, tolerability, PD and PK of venetoclax in combination with quizartinib, with the objectives of identifying the MTD and RP2D for each combination.

Quizartinib will be administered orally daily continuously starting on cycle 1 day 1. Patients will self-administer quizartinib tablets orally QD. If a dose is missed or vomited, the next dose should not be increased to account for missing a dose. The subject should take the next regular dose at the regularly scheduled time. Patients will receive one cycle of therapy every 28 days (+/- 7 days). Cycle 1 Day 1 of each cycle will be counted from the start of the quizartinib dosing. Quizartinib dose escalation criteria will be maintained as suggested in quizartinib Investigational Brochure (IB) as follows:

1. If the target dose for the given patient in the phase IB or phase II portion is quizartinib 30mg the patient will start the dosing on C1D1 at quizartinib 30mg per day
2. If the target dose for the given patient in the phase IB or phase II portion is quizartinib 60mg the patient will start the dosing on C1D1 at quizartinib 30mg per day and can increase to quizartinib 60mg per day on C1D12 only if QTcF on triplicate ECG is <450 msec on the Day 12 post-dose EKG

The initiation of venetoclax will be deferred for 7 days in cycle 1 to allow clinical and correlative evaluation of quizartinib single agent activity, and to debulk tumor burden thereby reducing the risk of tumor lysis syndrome (TLS). The intent is to initiate venetoclax on cycle 1 day 8. Blood samples will be collected at pre-dose, 2 (+/- 30 minutes), 4 (+/- 30 minutes), 6(+/- 30 minutes), 8 (+/- 30 minutes) and 24 (+/- 30 minutes) hours post-dose on cycle 1 day 14 to measure venetoclax, quizartinib and AC886 concentrations in patients enrolled in the dose-escalation period (n=12). The WBC count must be <10K prior to the initiation of venetoclax dosing. Note: Hydroxyurea can be used if needed during these initial 7 days to control WBC count, if needed.

It is suggested that each dose of venetoclax be taken with approximately 240 mL of water within 30 minutes after the completion of a low-fat breakfast. Examples of a low-fat breakfast include 2 slices of white toast with 1 tablespoon of low-fat margarine and 1 tablespoon of jam, and 8 ounces/240 mL of skim milk (319 calories and 8.2 g fat) or 1 cup/30 g of cereal, 8 ounces/240 mL of skim milk, 1 slice of toast with jam, 1 cup/240 mL of apple juice, and 1 cup/240 mL of coffee or tea (520 calories and 2 g fat). If vomiting occurs within 15 minutes after taking venetoclax and all expelled tablets are still intact, another dose may be taken. Otherwise, no replacement dose is to be taken. In cases where a dose of venetoclax is missed or forgotten, the patient should take the dose as soon as possible, ensuring that the dose is taken with food within 8 hours after the missed dose. Otherwise, the dose should not be taken. Patient compliance with the assigned daily dose of venetoclax will be assessed by standard pill counts. Bottles containing venetoclax tablets will be given to patients at regular scheduled visits. Previously distributed bottles will be returned to the clinic and tablets counted and returned study drug destroyed per institutional policy. Any discrepancy will be resolved with the patient at each clinic visit and documented in the patient record.

Any overdose or incorrect administration of Venetoclax and Quizartinib should be noted within Prometheus. Adverse events associated with an overdose or incorrect administration of study drug should be recorded as an Adverse Event within Prometheus.

- 5.1.1.1 Cycles may be started early (but not earlier than day 21) for patients with active disease if judged in the best interest of the patient.

*For the phase Ib, DLT defining period is 28 days. As such, cycle 2 should not be started before 28 days for the patients being treated on the phase Ib cohort to allow for adequate evaluation of DLTs.

- 5.1.1.2 Subsequent cycles may be delayed for recovery of toxicity or other medical conditions. Delays in start of subsequent cycles greater than 8 weeks will be acceptable only for patients who are deriving clinical benefit and after discussion with the principal investigator and the sponsor of potential risk/benefit ratio and complete documentation of the degree of clinical benefit and reason for continuation on this regimen.
- 5.1.1.3 In instances where one drug has to be discontinued transiently because of safety, the administration of the other drug may continue as scheduled. If the drug that is held can resume at a later time, no doses will be made up and the administration will follow the originally defined schedule calendar according to the drug that was continued.
- 5.1.1.4 For patients who discontinue therapy, the reason for treatment discontinuation will be documented.

5.2 Dose Adjustments

5.2.1 Venetoclax and quizartinib dose adjustments for drug-related hematological adverse events (AEs) (all dose adjustments to follow guidelines in section 5.2.2)

Dose reduction/interruption/discontinuation decisions should be based on the CTCAE version 5.0 of the toxicity and the guidelines provided below.

- Patients with acute leukemias usually present with abnormal peripheral blood counts at the time therapy is started and myelosuppression is an expected event during the course of therapy for acute leukemias. Thus, no dose adjustments or treatment interruptions for myelosuppression will be planned for the first 4 cycles and/or in the presence of residual leukemia. After that, treatment interruptions and dose adjustments may be considered according to the following guidelines only when there is no evidence of residual leukemia.
 - Patients with a response (no marrow evidence of leukemia) and pre-cycle counts of neutrophils $>1.0 \times 10^9/L$ and platelets $>50 \times 10^9/L$ who have sustained low counts of neutrophils $<0.5 \times 10^9/L$ or a platelet count $<20 \times 10^9/L$ for more than 2 consecutive weeks in the current cycle, are recommended to have the treatment with

venetoclax and/or quizartinib interrupted or dose-reduced by one dose level after discussing with the PI until neutrophils recover to $\geq 0.5 \times 10^9/L$ and platelets to $\geq 20 \times 10^9/L$. If prolonged myelosuppression defined as ANC $< 0.5 \times 10^9/L$ and platelets $< 20 \times 10^9/L$ (more than 8 weeks) with evidence of a hypocellular marrow (marrow cellularity less than 5% without evidence of leukemia) is observed in these patients, both venetoclax and quizartinib will be discontinued. Delays in start of subsequent cycles greater than 8 weeks will be acceptable only for patients who are deriving clinical benefit and after discussion with the principal investigator of potential risk/benefit ratio and complete documentation of the degree of clinical benefit and reason for continuation on this regimen.

- If there are persistent peripheral blood blasts, or the bone marrow shows $>5\%$ blasts or evidence of leukemia by other assays, treatment may be continued regardless of neutrophil and platelet count with supportive care as needed. Dose-interruptions of venetoclax and/or quizartinib in these patients should be considered on an individual case and discussed with the PI and the sponsor.
- Patients with a response (no marrow evidence of leukemia) and pre-cycle counts of neutrophils $< 1 \times 10^9/L$ and platelets $< 50 \times 10^9/L$ may be continued regardless of neutrophil and platelet count with supportive care as needed. Dose-interruptions in these patients should be considered on an individual case and discussed with the PI.
- Investigators should, whenever possible, determine which medication is causing the toxicity and interrupt or dose reduce venetoclax and/or quizartinib, as applicable.

5.2.2 Venetoclax and quizartinib dose adjustments for non-hematologic drug-related AEs

Investigators should, whenever possible, determine which medication is causing the toxicity and interrupt or dose reduce venetoclax and/or interrupt quizartinib, as applicable. Thus, if dose level +1 is established as the MTD (Table 1), one dose level reductions of quizartinib will be quizartinib 30 mg daily, two dose level reductions of quizartinib will be 20 mg daily, three dose reductions of quizartinib will be 15 mg daily, respectively. If the RP2D is lower than dose level +1 (Table 1) further dose reduction levels of quizartinib will be defined before moving to the phase II portion of the study.

Dose reductions of venetoclax for non-hematologic drug-related AEs will be as follows: assuming the starting dose = venetoclax 400 mg daily: one dose level reduction = 200 mg daily, two dose level reductions= 100 mg daily, three dose level reductions = 50 mg daily. The venetoclax dose will not be reduced beyond 50 mg daily. Reductions in the number of days of venetoclax, i.e. going from 28 day continuous dosing per cycle to 21-days on/7-days off schedule or a 14-days on/14-days off schedule will be allowed if this is felt to be in the best interest of the patient only after discussion and approval from the PI and clearly documenting the reason for the change in the schedule in the medical records of the patient.

During the dose escalation phase 1B dose-reductions will be allowed and will follow the schema outlined above.

Table 2 Dose adjustments for non-hematologic drug-related AEs, clinically significant in the opinion of the investigator (all dose adjustments to follow guidelines in section 5.2.2)

(The list of QTc prolonging medications is not comprehensive)

Grade	Occurrence	Dose modification
1 or 2	Any time	No dose reduction.
3 (Persistent grade 2: Consider similar dose adjustments if persistent and not responding to optimal management in the opinion of PI and treating physician)	1st time	Hold venetoclax and/or quizartinib. Resume venetoclax and/or quizartinib at prior dose if recovery to ≤ Grade 1 or baseline occurs within 14 days. If toxicity persists for 15-28 days, hold therapy and resume at ONE dose level below current dose for venetoclax OR quizartinib OR both based on which medication is likely causing the toxicity ONLY after recovery of toxicity to ≤ Grade 2. Dose re-escalation to prior dose of venetoclax OR quizartinib OR both is permitted if tolerated and no recurrent Grade 3 or 4 toxicities occur over 4 weeks while on the lower dose level.
	2nd time	Hold venetoclax and/or quizartinib. Follow until toxicity ≤ Grade 2. Resume at TWO dose level below current dose for venetoclax OR quizartinib OR both based on which medication is likely causing the toxicity ONLY after recovery of toxicity to ≤ Grade 2. Dose re-escalation by one dose level every 4 weeks of venetoclax OR quizartinib OR both is permitted if tolerated and no recurrent Grade 3 or 4 toxicities occur over the 4 weeks while on the lower dose level.

	3rd time	Stop venetoclax and quizartinib and discontinue patient. (For patients with clinical benefit/response from the combination we will consider continuation if toxicities resolve to ≤ grade 1 within 28 days and with proper dose adjustments after consultation with the PI and the sponsor.)
4	1st time	Hold venetoclax and/or quizartinib. Resume venetoclax and/or quizartinib at prior dose if recovery to ≤ Grade 1 or baseline occurs within 14 days. If toxicity persists for 15-28 days, hold therapy and resume at ONE dose level below current dose for venetoclax OR quizartinib OR both based on which medication is likely causing the toxicity ONLY after recovery of toxicity to ≤ Grade 2. Dose re-escalation to prior dose of venetoclax OR quizartinib OR both is permitted if tolerated and no recurrent Grade 3 or 4 toxicities occur over 4 weeks while on the lower dose level.
	2 nd time	Stop venetoclax and quizartinib and discontinue patient. (For patients with clinical benefit/response from the combination we will consider continuation if toxicities resolve to ≤ grade 1 within 28 days and with proper dose adjustments after consultation with the PI and the sponsor.)
Cardiac Toxicity	Grade 1 QTc ≥ 450 and ≤ 480 msec	Check magnesium and potassium levels and correct any abnormalities. If possible, stop any medications that may prolong the QTc interval. Continue quizartinib at the same dose.
Cardiac Toxicity	Grade 2 QTc > 480 and ≤ 500 msec	Check magnesium and potassium levels and correct any abnormalities. If possible, stop any medications that may prolong the QTc interval. The dose of quizartinib will be reduced one level without interruption of dosing. Following dose reduction, the quizartinib dose may be resumed at the previous level in the next cycle if the QTc has decreased to within 30 msec of baseline or <450 msec but subject must be monitored closely for QT prolongation for the first cycle at the increased dose. Subjects who experience >480 msec QTc prolongation and undergo dose interruption and/or reduction must be monitored closely with ECGs, performed twice weekly for the first week of the QTc prolongation and then weekly thereafter until the QTc prolongation is resolved.

Cardiac Toxicity	Grade 3 QTc interval >500 msec (at least on two separate EKGs) or >60 ms change from baseline	Check magnesium and potassium levels and correct any abnormalities. Interrupt quizartinib and if possible any medications that may prolong the QTc interval. Quizartinib dosing will be interrupted for up to 14 days. If QTcF returns to within 30 msec of baseline or <450 msec within 14 days, quizartinib administration may be resumed at a reduced dose (reduce by one level). Subjects who experience >500 msec QTcF prolongation and undergo dose interruption and/or reduction must be monitored closely with ECGs, performed twice weekly for the first week of the QTcF prolongation and then weekly thereafter until the QTc prolongation is resolved.
Cardiac Toxicity	Grade 4 , and Torsade de pointes or polymorphic ventricular tachycardia or signs/symptoms of serious arrhythmia (i.e., grade 4)	Quizartinib dosing will be permanently discontinued

- If the criteria to resume treatment are met, the subject should restart treatment at the next scheduled time point per protocol. However, if the treatment is delayed past the next scheduled time point per protocol, the next scheduled time point will be delayed until dosing resumes.
- Patients in whom the toxicity occurs or persists beyond the planned completion of drug administration for the cycle will have the dose reductions for either venetoclax or quizartinib or both agents (based on attribution of the specific toxicity to venetoclax or quizartinib or both) implemented in subsequent cycles provided the toxicity has resolved as specified in Table 2 above.
- These general guidelines constitute guidance to the Investigator and may be supplemented by discussions with the PI in specific cases.
- Guidelines for dose adjustment for toxicities that are may be reasonably related to venetoclax are given below.

5.2.3 Intra-patient dose escalation

Intra-patient dose escalation of venetoclax and quizartinib (in accordance with the dosing schema in Table 1) will be permitted provided:

- Patient has completed ≥ 1 cycle at their current dose level
- Patient has not experienced any grade 3 or higher non-hematologic drug-related toxicity (including Grade 3 QTcF prolongation), and
- Patient has not experienced hematologic DLT, and
- At least 6 patients have been treated at the next higher dose level and followed for at least 28 days without experiencing DLT and this dose level has been deemed safe and does not exceed the RP2D.
- The dose may be escalated by one dose level per cycle (per Table 1) provided such dose level does not exceed RP2D.
- Dose escalation of only one of the two agents is allowed if judged in the best interest of the patient (e.g., in patients with neutropenia this would be likely secondary to venetoclax, in patients with QTc changes this would be likely secondary to quizartinib).
- However, the dose of any agent cannot be escalated beyond the established RP2D for the combination.

5.2.4 Modifications of dose schedules other than the above will be allowed within the following guidelines:

5.2.4.1 Further dose reductions can be made to keep clinically significant toxicities grade ≤ 2 .

5.2.4.2 Dose adjustments by more than 1 dose level at a time (e.g., from quizartinib 60 mg daily to 20 mg daily) can be considered when judged in the best interest of the patient (e.g. severe myelosuppression or other toxicity attributable to one of the agents) when toxicity has resolved. The reason for this reduction will be discussed with the PI or Co-PI and documented in the medical record.

5.2.4.3 A patient who has had a dose reduction because of any of the reasons mentioned above may have their dose escalated provided the patient has remained free of toxicity requiring dose adjustments as defined above for at least 1 month. Escalation will be made by 1 dose-level increment only, and not more frequent than every month.

5.2.4.4 Treatment interruptions and dose modifications other than the ones mentioned above can be considered after discussion with the PI and proper documentation of the rationale. Dose adjustment/delay of only one of the agents is permissible if the toxicity is most likely judged to be related to one of the agents by the investigator (e.g., in patients with

prolonged neutropenia this would be likely secondary to venetoclax, in patients with QT changes this would be likely secondary to quizartinib).

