The major circulating moieties are unchanged quizartinib and AC886 (> 10% of the total radioactivity exposure in plasma). AC886 has similar potency and selectivity to quizartinib and has been measured in all clinical studies with quizartinib PK assessments. The median Tmax for AC886 ranged from approximately 5 to 8 hours across studies in healthy volunteers. The ratio of AC886 to quizartinib (AUClinf) was approximately 0.5 at steady state.

Elimination: The principal route of excretion was hepatobiliary, estimated as > 90%. Renal excretion was a minor route of elimination (< 2%). The terminal elimination half-lives for quizartinib and AC886 are approximately 100 hours. For quizartinib 60 mg QD, the observed geometric mean accumulation ratios (AUC0-24h) for quizartinib and AC886 were 5.7 and 8.2, respectively.

Safety

A cardiovascular safety pharmacology study in cynomolgus monkeys demonstrates that single oral doses of quizartinib result in prolonged QTc interval at ≥ 10 mg/kg doses and biologically significant increased systolic blood pressure at ≥ 100 mg/kg doses. It should be noted that increases in blood pressure were not observed in the Phase 1 dose-escalation study, Protocol AC220-CP0001; henceforth called Study CP0001(33). No QTc interval prolongation was evident in monkeys dosed with 3 mg/kg quizartinib. It is suggested that quizartinib and AC886 induced blockade of human ether-à-go-go-related gene (hERG) current and I_{Ks} , and therefore caused QT prolongation by a decrease in the net repolarization currents. The effect on I_{Ks} was more dominant than that on hERG. There were no apparent electrocardiogram (ECG) abnormalities in the dog (28- and 90-day) or monkey (28- and 90-day) general toxicology studies. In addition, there were no apparent toxicologically relevant quizartinib-related heart microscopic changes in the rat, dog, or monkey general toxicology studies.

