3.5 Phase II expansion

Once MTD is defined, the RP2D will be selected based on efficacy, safety, and pharmacodynamics data evaluation from the phase Ib in discussion with the PI, Co-PI, sponsor and supporting companies (Daiichi-Sankyo, Abbvie and Genentech). The PI is responsible for completing the cohort summary template prior to advancing subjects to the phase II portion. The phase II portion will have 20 patients. Any patients still on study from the phase I portion at a dose lower than RP2D can be dose escalated up to RP2D in accordance with the dose escalation guidelines in section 5.2.3.

However, the dose for any patient may never exceed the RP2D.

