- 7.2.8 EKG will be performed on day 1, day 5, day 8, and day 12 of the first cycle (all ± 2 days) Day 1 and day 8 ECG are collected pre-dose; day 5 are collected pre-dose and 4 hrs (+/- 2 hrs) post-dose; day 12 are collected 4 hrs (+/- 2 hrs) post-dose. Then ECG to be done on day 1 of each cycle for cycles 2, 3, 4 and 5 before initiation of quizartinib and 4 hr (+/- 2 hrs) post dose, then pre-dose every 2 subsequent cycles. EKG may be omitted if patient has not received study drug (quizartinib) in the 48 hrs preceding the time when EKG is done. EKG at screening and for the first 3 cycles will be done in triplicate. Subjects **should rest in the supine position or semi-recumbent, with the same position used for an individual subject for the duration of the study, for at least 5 minutes before each 12-lead ECG recording is started. The ECGs should be reviewed, signed,**

and dated by a qualified physician (or qualified physician's assistant or nurse practitioner) and any clinically important finding recorded on the appropriate eCRF. The results will include heart rate, PR interval, QRS interval, QT interval, and QTcF interval. QTcF is calculated using the formula, $(QT)/3\sqrt{RR}$. All screening and on study ECGs should be obtained in triplicate (10 seconds for each ECG over the 5-minute period).

- A. On patients who increase the dose of Quizartinib or start therapy with a drug that is a moderate CYP3A4 inhibitor, an EKG will be required 24 hrs (± 6 hrs), 7 days (± 2 days) and 14 days (± 2 days) after the dose increase or after the start of the moderate CYP3A4 inhibitor.
- B. Patients who had their dose reduced because of QTc prolongation and have their dose re-escalated as described in section 5.2.3 will have an EKG repeated 24 hrs (± 6 hrs) and 7 days (± 2 days) after re-escalation.
- C. The QTc interval will be calculated by Fridericia's correction factor (QTcF). The 12-lead EKG evaluation will consist of 3 separate EKGs obtained at least 5 minutes apart.

7.2.9 Peripheral blood (up to 40 cc each time) and bone marrow (up to 15 cc each time) for pharmacodynamic studies (Optional) as defined in section 6.0 on

Peripheral blood:

- Prior to first dose of quizartinib at baseline (Cycle 1 Day 1).
- Cycle 1 Day 8: prior to the first dose of venetoclax
- Cycle 1 Day 15: prior to the dose of quizartinib and venetoclax (steady state)
- Cycle 1 Day 28 (+/- 4 days): prior to the dose of quizartinib and venetoclax
- At progression/relapse (if sample available)

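### If the RP2D is quizartinib 60 mg, Section 5.2.3 lets phase Ib patients on 30 mg move up without the QTcF <450 msec check that Section 5.1 sets for the same step on Day 12

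*Combined protocol and SAP*

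**What the plan says.** **Day 12 step (Section 5.1).** A patient whose target is 60 mg starts at 30 mg; that patient "can increase to quizartinib 60mg per day on C1D12 only if QTcF on triplicate ECG is <450 msec on the Day 12 post-dose EKG". This rule is tied to that day and to patients with that target.

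**Later increases (Sections 3.5, 11.1 and 5.2.3).** Section 3.5 states: "Any patients still on study from the phase I portion at a dose lower than RP2D can be dose escalated up to RP2D", following 5.2.3; Section 11.1 repeats this. Section 5.2.3 allows one Table 1 level per cycle, which from 30 mg means 60 mg. It requires at least one completed cycle at the current level, no hematologic DLT, and a next level that six patients have completed for 28 days without DLT, that is deemed safe and that does not exceed the RP2D. Its QTc condition is "Patient has not experienced any grade 3 or higher non-hematologic drug-related toxicity (including Grade 3 QTcF prolongation".

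**QTc management (Section 5.2.2, Table 2).** At Grade 1 (450-480 msec) the instruction is "Continue quizartinib at the same dose". At Grade 2 (above 480, up to 500 msec) the dose drops one level and may later be "resumed at the previous level in the next cycle if the QTc has decreased to within 30 msec of baseline or <450 msec". Grade 3 is above 500 msec or a change of more than 60 msec from baseline.

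**ECGs (Section 7.2.8).** After a quizartinib increase, "an EKG will be required 24 hrs (± 6 hrs), 7 days (± 2 days) and 14 days (± 2 days" later. The routine schedule is: "Then ECG to be done on day 1 of each cycle for cycles 2, 3, 4 and 5 before initiation of quizartinib" and again about 4 hours post-dose, then pre-dose every second cycle. No QTcF limit for escalation is attached to any of these.

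**The concern.** The same step, 30 mg to 60 mg, is held to a current QTcF limit on Day 12 and to none afterwards. A dose level 0 patient has a 30 mg target, so the Day 12 rule never applies to that patient; 5.2.3 is the only stated route to 60 mg, and it looks only at whether a Grade 3 event has already happened.

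QTc prolongation is the toxicity that Section 2.2 names as dose-limiting for quizartinib. Quizartinib also clears slowly, so an increase that proves unwise cannot be undone quickly. Item B of 7.2.8 adds to the difficulty: it points to 5.2.3 for re-escalation after a QTc-related reduction, so a reader looking there for the QTc rule finds no threshold.

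**Working it through.** The core of the check is a comparison of rules; the arithmetic only shows what the later ECGs can and cannot do.

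**1. The routes to a higher dose, side by side**

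| Route | Applies to | QTc condition before the dose is given |
|---|---|---|
| 5.1, Day 12 | Target dose 60 mg | Triplicate post-dose QTcF <450 msec |
| Table 2, after Grade 2 | Dose reduced at >480 to 500 msec | Within 30 msec of baseline, or <450 msec |
| 5.2.3 | Below the RP2D, at least one cycle completed | No earlier Grade 3 event; no current limit, no ECG required |

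**2. Who falls between the rules.** Section 5.1 withholds 60 mg at 450 msec or more. Section 5.2.3 bars only Grade 3. Between 480 and 500 msec, Table 2 reduces the dose and applies its own test before resuming. What remains is a QTcF of 450-480 msec with a change from baseline of no more than 60 msec. Such a patient is 500 - 480 = 20 to 500 - 450 = 50 msec below the 500 msec limit.

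**3. Size of the exposure step (Section 2.2, steady-state geometric means).** AUC0-24h: 8276 / 3370 = 2.46-fold. Cmax: 487 / 186 = 2.62-fold.

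**4. What the ECGs after the increase see.** Section 2.2 gives: "The terminal elimination half-lives for quizartinib and AC886 are approximately 100 hours". Assuming first-order elimination with half-life T, the share of the added exposure reached at time t is 1 - 2^(-t/T). With T = 100 h:

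- 24 h: 1 - 2^(-0.24) = 0.153
- 7 days (168 h): 1 - 2^(-1.68) = 0.688
- 14 days (336 h): 1 - 2^(-3.36) = 0.903

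For a range, solve the accumulation ratios in Section 2.2, R = 1 / (1 - 2^(-24/T)). R = 5.7 (quizartinib) gives T = 86.2 h; R = 8.2 (AC886) gives T = 127.9 h. The shares are then 12-18% at 24 h, 60-74% at 7 days and 84-93% at 14 days. Exposure rises somewhat more than in proportion to dose (2.46-fold for a doubling), so these are approximations. After a stop, exposure takes 100 / 24, or about 4 days, to halve.

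The 7-day and 14-day ECGs are therefore informative. The 24-hour ECG is a weak substitute for a check beforehand, and all three come after 60 mg has started.

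**5. What the documents show about risk.** In the randomized phase 2 comparison in Section 2.2 (38 patients per arm), maximum QTcF change above 60 msec occurred in 3% at 30 mg and 19% at 60 mg. QTc above 500 msec occurred in 5% at 30 mg and 3% at 60 mg: 0.05 × 38 = 1.9 and 0.03 × 38 = 1.1, about two patients against one. The first measure points to a dose effect; the second shows none and is too sparse to settle the matter. No figure is given for patients who go to 60 mg while at 450-480 msec.

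**The case against.** The strongest reply is that Table 2 already deals with this range: at 450-480 msec the patient is to stay on the same dose, and raising the dose is not that. Since an increase under 5.2.3 follows a completed cycle, one made at the start of cycles 2-5 would meet a scheduled Day 1 ECG. This has weight; Table 2 does point against escalating. It does not close the gap, because the notes below Table 2 call its rules guidance, 5.2.3 does not refer to it, and it neither requires an ECG before an increase nor sets a limit for one.

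Other points stand in part:

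- Escalation is permitted, not required, so an investigator can decline it. That leaves the limit to judgment where 5.1 does not.
- Section 5.1 says its criteria follow the quizartinib Investigator's Brochure, which is not among the documents. If the brochure covers later increases, 5.2.3 does not carry that over.
- The protocol has no single 450 msec standard. Screening allows a baseline up to 450 msec, so Table 2 can allow resumption at 450 + 30 = 480 msec. But that is a return to a dose already taken; for a first step to 60 mg, the only limit the protocol states is 5.1's.
- The reach is small: mainly the six planned dose level 0 patients, and of those only the ones still on study once dose level +1 has been cleared.

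A reader might infer that patients assigned to 60 mg but held at 30 mg on Day 12 can later be raised under 5.2.3. The documents do not support this as fact. Those patients are already assigned to the top level of Table 1, and 5.1 gives them no second opportunity. The text simply does not say clearly whether a later increase is allowed.

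**Conclusion.** The gap is real but narrow. If the RP2D is 60 mg, which is the stated target dose, 5.2.3 as written allows a dose level 0 patient to start 60 mg at a QTcF at which 5.1 would withhold it, with no required ECG beforehand. It should be corrected, as a matter of consistent safety wording.

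Two stronger conclusions are not supported. One is that the omission exposes patients to a known excess of severe QTc prolongation: the size of the risk is not known, and the rates above 500 msec show no dose difference. The other is that the six-patient clearance of 60 mg is undermined because held patients may count towards it. That turns on how the 75% dosing rule in Section 3.4 is read and on how many patients are held, for which no figure is given. It is a separate question and no change is proposed here.

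The finding about the rules rests on the text alone. The exposure shares rest on first-order elimination and a half-life of about 100 hours (86-128 h as a range). Confidence is medium, chiefly because Table 2 can be read as discouraging the increase and the brochure is not available.

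**What to change.** Add to the conditions in Section 5.2.3:

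*Triplicate post-dose QTcF <450 msec at the current dose is required before any first increase to quizartinib 60 mg, including any later increase in a patient held at 30 mg by the Day 12 rule.*

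Table 2 keeps its own rule for resuming a dose that was reduced for QTc. The sponsor should also state whether a held patient may be raised later at all; the sentence only sets the condition if so.

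In cycles 2-5 the scheduled Day 1 ECG, which includes a reading about 4 hours post-dose, can serve, with 60 mg starting the next day. The word triplicate should stay in the sentence, because 7.2.8 says in one place that triplicates cover screening and the first three cycles and in another that they cover all on-study ECGs. From cycle 6, when routine ECGs are pre-dose and every second cycle, at most one ECG is added per escalation.

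The cost is protocol wording. No patients are added. A few later escalations would be delayed or refused.
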